8.3. VITAL SIGNS

Vital signs are to be assessed at Screening, Baseline, Week 2 and Months 1, 2, 4 and every 12 months thereafter.

Observed and change from baseline data will be summarized using descriptive statistics for Months 2 and 4.

In addition to summarizing by visit the last ‘on-treatment’ measurements will also be summarized. The last ‘on-treatment’ measurement must be after Day 1 and within 1 day of the final dose of LIQ861.

Vital signs data will be listed, with changes from baseline values included.

8.4. PHYSICAL EXAMINATION

All abnormal findings at Baseline will be recorded on the Medical History/Concomitant Diagnoses page (or equivalent) of the case report form. New abnormal findings or a worsening of baseline conditions detected at follow-up physical examinations will be recorded as AEs on the eCRF.

Physical examination data will be listed.

9. EXPLORATORY ENDPOINTS

9.1. SIX-MINUTE WALK DISTANCE

Six-minute walk distance is to be assessed at Screening, Baseline, Week 2 and Months 1, 2, 4 and every 4 months thereafter.

6MWD and changes from baseline will be summarized by visit (Week 2 and Months 2, 4 and 8). For the changes from baseline the 95% confidence intervals for the mean changes will also be presented. Mean changes from baseline and 95% CIs will be plotted against visit for each Group.

The changes from baseline in 6MWD to Month 8 will be analyzed using a mixed effect model for repeated measures (MMRM) with group, visit and group-by-visit interaction as fixed effects and baseline as a covariate. An unstructured covariance will be attempted, but alternative structures will be explored if the unstructured structure isn't suitable. The Kenward-Roger method will be used to adjust the degrees of freedom. Comparisons of the least square means for the interaction term, group-by-visit, will provide inferential statistics for comparisons between groups at Months 2, 4 and 8.

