9.3. NT-proBNP

NT-proBNP will be assessed at Screening, Baseline, Week 2 and Months 1, 2, 4 and every 4 months thereafter.

Values and changes from baseline will be summarized by visit (Week 2 and Months 2, 4 and 8). Geometric means will be included for the absolute values and the ratio to baseline from back-transforming the mean changes from baseline for natural log data will be presented for the changes from baseline. The 95% confidence intervals will also be presented for the ratios. The ratios and 95% CIs will be plotted against visit for each group.

Values and changes from changes from baseline will also be summarized for the age sub-groups (<75 years of age and \geq 75 years of age).

The change from baseline in NT-proBNP to Month 8 will be analyzed using an MMRM analysis with group, visit and group-by-visit interaction as fixed effects and baseline as a covariate. An unstructured covariance will be attempted, but alternative structures will be explored if the unstructured structure isn't suitable. The Kenward-Roger method will be used to adjust the degrees of freedom. Comparisons of the least square means for the interaction term, group by visit, will provide inferential statistics for comparisons between groups at Months 2, 4 and 8. Given that the data are skewed with some subjects having very high values, a natural log transformation will be applied to the data prior to analysis. Consequently back-transformed LS means will provide ratio comparisons of the groups.

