9.4. MLWHF QUALITY OF LIFE QUESTIONNAIRE

The MLWHF Quality of Life Questionnaire will be assessed at Baseline, Month 2, Month 4 and every 12 months thereafter. The Questionnaire has 21 items, each scored within the range 0 to 5. Two domains and 1 total score will be derived:

- Physical Dimension (Range 0 to 40)
- Emotional dimension (Range 0 to 25)
- Total Score (Range 0 to 105)

Higher scores denote poorer quality of life. The scores are provided by the site in the eCRF. The scores will be used as provided, even if answers to some of the individual questions are missing.

Scores and changes from baseline will be summarized by visit (Months 2, 4 and 8).

The changes from baseline to Month 8 will be analyzed using an MMRM analysis with group, visit and group-by-visit interaction as fixed effects and baseline as a covariate. An unstructured covariance will be attempted, but alternative structures will be explored if the unstructured structure isn't suitable. The Kenward-Roger method will be used to adjust the degrees of freedom. Comparisons of the least square means for the interaction term, group-by-visit, will provide inferential statistics for comparisons between groups at Months 2, 4 and 8.

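### The 6MWD and NT-proBNP MMRMs hold the baseline slope constant over visits, which can bias the Month 8 group comparison if that slope changes and the non-randomised groups differ at baseline

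*SAP*

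**What the plan says.** SAP 9.1 specifies, for change in 6MWD to Month 8, a "mixed effect model for repeated measures (MMRM) with group, visit and group-by-visit interaction as fixed effects and baseline as a covariate". For NT-proBNP, SAP 9.3 gives the same terms over the same period, as an "MMRM analysis with group, visit and group-by-visit interaction as fixed effects and baseline as a covariate", and adds that "a natural log transformation will be applied to the data prior to analysis". SAP 9.4 repeats the model for MLWHF: "The changes from baseline to Month 8 will be analyzed using an MMRM analysis with group, visit and group-by-visit interaction as fixed effects", again with baseline as a covariate. None of the three sections lists an interaction of baseline with visit.

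On the covariance, SAP 9.1 says: "An unstructured covariance will be attempted, but alternative structures will be explored". Degrees of freedom follow Kenward-Roger. The LS-mean comparisons from the group-by-visit term "will provide inferential statistics for comparisons between groups at Months 2, 4 and 8".

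SAP 6.1 states that the two groups differ by treatment history before entry, and that there is no formal hypothesis testing. Under SAP 9.1 and 9.3, 6MWD and NT-proBNP are collected at Week 2 and Months 1, 2, 4 and 8. Under SAP 9.4, MLWHF is collected at Months 2 and 4 and then every 12 months, so its next scheduled visit is Month 16.

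**The concern.** The model lets the group effect vary by visit but not the effect of baseline. The slope of change on baseline is therefore assumed to be the same two weeks after the start as at Month 8. When the correlation with baseline weakens over time and the spread stays similar, the slope for a change score becomes more negative at later visits. A single fitted slope then adjusts too little at Month 8.

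In a randomised trial this would matter little for a group contrast, because the mean baselines would be about equal. Here nothing in the design balances them: one group enters on stable inhaled treprostinil, the other on no more than two oral therapies. Any adjustment error is multiplied by whatever baseline gap exists. The unstructured covariance and the Kenward-Roger adjustment act on the residual covariance and the degrees of freedom, so they do not relax the restriction on the mean. At stake are the adjusted Month 8 results, from the last visit modelled in a long-term study.

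**Working it through.** **No figure to reproduce.** The documents state no SD, correlation, effect size or LS mean for these models.

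**Inputs from the documents.** Fixed effects as quoted. Groups of 55 Transition and 65 Add-On (SAP 5.3, Efficacy Population; SAP 9.1 to 9.4 name no population for these models, so its use is an assumption). Visits Week 2 and Months 1, 2, 4 and 8 (inferred from the assessment schedule; the SAP does not list the MMRM visits).

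**Assumed inputs for 6MWD.** SD 100 m at every visit; baseline-to-visit correlation 0.95 × exp(−λ × months), with λ = 0.01, 0.03 or 0.05; baseline difference D (Transition minus Add-On) of 20, 40 or 60 m; true adjusted group difference 0.

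**Formulas.** With saturated group-by-visit means and complete data:

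- slope at visit t with equal SDs: b_t = correlation_t − 1
- common slope: b* = 1′S⁻¹b / 1′S⁻¹1, with b the visit slopes and S the residual covariance
- contrast bias at visit t = (b_t − b*) × D
- LS-mean bias = contrast bias × the other group's share of N, with opposite signs in the two groups

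**Middle case, λ = 0.03.** The slopes are −0.064, −0.078, −0.105, −0.157 and −0.253, and b* = −0.086. At Month 8 with D = 40 m: (−0.253 + 0.086) × 40 = −6.7 m. The LS means shift by −6.7 × 65/120 = −3.6 m (Transition) and +6.7 × 55/120 = +3.1 m (Add-On). Over the three decay rates, Week 2 and Month 1 carry about 67 to 83% of the weight in b*, which is why Month 8 is furthest from it.

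**Contrast bias for D = 40 m:**

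| λ per month | Month 2 | Month 4 | Month 8 | Month 8 bias / SE | Month 8 coverage of 95% CI |
|---|---|---|---|---|---|
| 0.01 | −0.1 m | −0.9 m | −2.3 m | 0.26 | 94.2% |
| 0.03 | −0.8 m | −2.9 m | −6.7 m | 0.55 | 91.5% |
| 0.05 | −1.4 m | −4.6 m | −10.3 m | 0.73 | 88.8% |

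Bias is proportional to D. The smallest Month 8 value is 2.3 × 20/40, about 1.2 m (0.13 SE). The largest is 10.26 × 60/40 = 15.4 m (1.09 SE). In that largest case the bias is about 2 m at Week 2 and Month 2, and 6.9 m at Month 4.

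**Second set of assumptions.** SD 110 m, no Month 1 visit, Month 8 slope −0.175 (mild) or −0.261 (steeper), common slope near −0.10. For D = 20 to 60 m the Month 8 bias is 1.5 to 4.6 m (mild, SE 11.4 m) or 3.2 to 9.6 m (steeper, SE 13.6 m).

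**NT-proBNP.** Assumed log SD 1.3, log baseline difference 0.5, correlation 0.90 × exp(−λ × months). Month 8 bias is (−0.292 + 0.145) × 0.5 = −0.07 log units for λ = 0.03, and (−0.397 + 0.169) × 0.5 = −0.11 for λ = 0.05. The ratio is off by about 7 to 11% (0.44 to 0.60 SE).

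**MLWHF.** Assumed SD 24, difference 10 points, Months 2 and 4 only. The largest bias is (−0.345 + 0.305) × 10 = −0.4 points, about 0.1 SE.

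**When the bias is zero.** If b_t is the same at every visit, the bias is 0 even for D = 60 m. If D = 0, it is 0 with complete data even when slopes vary; simulations with dropout showed none of note.

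**With baseline-by-visit added** (simulated, D = 40 m). For λ = 0.03 the Month 8 bias falls from −6.9 to −0.5 m, or from −7.0 to −0.7 m with dropout that depends on the last value. For λ = 0.05 it falls from −10.0 to +0.7 m, and coverage rises from 88.5% to 93.5%. The empirical SD of the contrast barely moves (12.31 vs 12.30 m; 15.1 vs 15.0 m).

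**The case against.** The strongest reply is that every size above is assumed. The slope of change on baseline is correlation × (SD at visit / SD at baseline) − 1, so it equals correlation − 1 only when the SDs are equal. In the mild case of the second set, the Month 8 correlation is about 0.825. If the Month 8 SD were 10% above baseline, the slope would be 0.825 × 1.10 − 1 = −0.09, close to the common slope of about −0.10, and the bias would nearly vanish. This stands: a reader might infer that the slope must steepen with time, and that does not follow.

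The second reply is that little rests on these contrasts. The primary endpoint is adverse events, Protocol 6.1.2 says that the study is not designed for efficacy conclusions, and both groups receive LIQ861. SAP 9.1 and 9.3 also plan observed changes (ratios for NT-proBNP) with confidence intervals by group and visit, which do not use the common slope. This too stands and limits the importance of the point. It does not dispose of it, because the SAP itself describes the model contrasts as inferential and the remedy is one term.

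Third, a reader might infer that MLWHF is equally affected, since the model text is the same. The schedule does not support that. Any Month 8 MLWHF value would have to come from a termination or unscheduled assessment, and over Months 2 and 4 the restriction hardly matters.

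**Conclusion.** The restriction is real in SAP 9.1 and 9.3, and it can bias the LS means and group contrasts for 6MWD and NT-proBNP, mainly at Month 8. Two conditions must hold together: the groups differ at baseline, and the slope varies over visits. A reader might infer that non-randomised groups alone produce the bias. They do not, and the documents show neither condition.

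For 6MWD the Month 8 contrast error is about 1 to 15 m (0.1 to 1.1 SE) over the assumed ranges. The upper end needs both the fastest decay tried and a 60 m baseline gap. All these sizes rest on equal SDs across visits, assumed correlations and baseline gaps, and 55 and 65 patients. The point is a worthwhile improvement to an exploratory analysis. It has no bearing on the safety objective.

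**What to change.** In SAP 9.1 and 9.3, add a baseline-by-visit interaction to the fixed effects (log baseline by visit for NT-proBNP) and leave the rest of each model as it is. List the visits that enter the model. SAP 9.4 may take the same term for consistency only.

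The cost is one parameter for each visit after the first: four if Week 2 and Months 1, 2, 4 and 8 are all modelled, three without Month 1. With about 120 patients the simulations showed almost no loss of precision. SAP section 2 allows amendment before database lock.

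The term corrects only the form of the baseline adjustment. Transition and Add-On still differ by prior therapy, so the report should present the contrasts as exploratory comparisons of non-randomised groups.

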8.4. Hypothesis

No formal hypothesis testing is planned.

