3.4. TREATMENT ASSIGNMENT AND BLINDING

All subjects will receive open label LIQ861 and doses according to their individualized titration.

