4.4. EXPLORATORY ENDPOINTS

For all patients:

- Change from Baseline to Week 2 and Months 1, 2, 4 and every 4 months thereafter in 6MWD
- Change from Baseline to Week 2 and Months 1, 2, 4 and every 4 months thereafter in NYHA Functional Class status
- Change from Baseline to Week 2 and Months 1, 2, 4 and every 4 months thereafter in NT-proBNP levels
- Change from Baseline to Month 2, Month 4, and every 12 months thereafter in the Minnesota Living with Heart Failure (MLWHF) Quality of Life Questionnaire
- Time to and reason for discontinuation of LIQ861

For transitioning from Tyvaso only:

- Proportion of patients maintaining a sustained treatment transition through the end of Month 2. Sustained treatment transition is defined as meeting the following conditions: 1) current treatment with LIQ861 through at least 2 months beyond transition from Tyvaso, 2) no interruptions to study treatment totaling more than 7 days prior to the end of Month 2, and 3) no treatment with any prostacyclin or prostacyclin analogs apart from administration of LIQ861.
- Comparison of LIQ861 dose achieved at sustained treatment to previous Tyvaso dose.
- Patient satisfaction with the LIQ861 DPI compared to the inhalation device from which they are transitioning from using a simple questionnaire to assess device preference.

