6. GENERAL ASPECTS FOR STATISTICAL ANALYSIS

6.1. GENERAL METHODS

Subjects differ by treatment history prior to entry to Study LTI-301 - the two groups will be referred to as the Transition and Add-On Groups. For all summary tables data will be presented for all subjects (Overall) and by group.

Continuous variables will be summarized using the number of non-missing observations (n), mean, standard deviation (SD), standard error (SE), median, minimum and maximum. Categorical variables will be summarized using frequencies and percentages.

Categorical shift tables will include marginal totals.

Unless otherwise specified, the estimated mean and median for a set of values should be printed out to 1 more decimal place than the original values, and SD and SE should be printed out to 2 more decimal places than the original values. The minimum and maximum should report the same number of decimal places as the original values.

Percentages will be displayed with 1 decimal place; except percentages will not be presented when the count is zero and 100% will be presented as an integer. The number of subjects in the analysis population will be the denominator.

Unless stated otherwise, baseline will be taken as the last available non-missing assessment prior to study drug administration (Day 1).

In by-visit summary tables, the baseline will be summarized using all available data, but also for each visit using only the baseline data from subjects with available data at the visit; hence the mean change from baseline will equal the mean visit value – mean baseline value.

Throughout this document ‘change from baseline’ refers to the actual change from baseline (i.e. visit value – baseline value).

All data will be listed separately for each group. Data listings will present study days in addition to dates, where study day is derived as (assessment date – first day of dosing + 1).

Since there is no formal hypothesis testing, no adjustment for multiplicity will be made for inferential statistical comparisons within or between groups.

Programming of analyses, tables and listings will be performed using R Version 3.4.0 or higher (R Foundation for Statistical Computing, Vienna, Austria) or SAS® Version 9.3 or higher (Cary, North Carolina, US).

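### The only named output of the 6MWD, NT-proBNP and MLWHF mixed models is a Transition-versus-Add-On comparison that prior treatment confounds and no endpoint uses; the model-based within-group change is not a stated output

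*SAP*

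**What the plan says.** SAP 9.1, 9.3 and 9.4 each fit an MMRM to change from baseline, with "group, visit and group-by-visit interaction as fixed effects and baseline as a covariate". Each section then states what the model is for: comparisons of the group-by-visit LS means that "will provide inferential statistics for comparisons between groups at Months 2, 4 and 8". Section 9.3 ends: "Consequently back-transformed LS means will provide ratio comparisons of the groups".

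Other statements bear on that output:

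- SAP 6.1 on the two groups: "Subjects differ by treatment history prior to entry to Study LTI-301". SAP 3.4: "All subjects will receive open label LIQ861 and doses according to their individualized titration". Nobody is randomised between Transition and Add-On.
- SAP 4.4 defines the 6MWD endpoint as "Change from Baseline to Week 2 and Months 1, 2, 4 and every 4 months thereafter in 6MWD", listed for all patients. NT-proBNP and MLWHF are worded in the same way, and none names a group contrast.
- The objectives (SAP 3.1) are long-term safety and tolerability, and comparative bioavailability of two inhaled formulations.
- Protocol 8.4: "No formal hypothesis testing is planned". SAP 6.1 gives this absence of formal testing as its reason that "no adjustment for multiplicity will be made for inferential statistical comparisons within or between groups".
- Outside the models, SAP 9.1 plans observed mean changes in 6MWD with 95% CIs, and SAP 9.3 plans NT-proBNP ratios to baseline with 95% CIs, both plotted by group. SAP 9.4 plans only a summary of MLWHF scores and changes, with no interval.

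**The concern.** Protocol 3.1 defines Transition patients as stable on Tyvaso for at least 3 months. Add-On patients take no more than two oral therapies, none of them a prostacyclin. Change from baseline therefore measures different things. In Transition it is the result of replacing one inhaled treprostinil product with another. In Add-On it is the result of adding inhaled treprostinil. A difference between the two is expected and says nothing about whether LIQ861 works better in one group.

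If the models are run and reported as written, a smaller change in Transition could be misread as LIQ861 working less well there. The quantity the endpoints describe, change from baseline, would not be a required output of the model. That matters because the planned observed-change summaries use only subjects with data at the visit (SAP 6.1), without imputation (SAP 6.2). The MMRM is the one planned analysis that uses all the repeated measures under a missing-at-random assumption.

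**Working it through.** The plan has no figure of its own to reproduce here. It states no alpha, power, SD or target difference for these contrasts, and its sample-size figures (130 enrolled so that 100 complete 2 months, SAP 3.3) concern safety.

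**1. What the contrast estimates when LIQ861 acts identically.** Let t be the effect of inhaled treprostinil against none, the same for both products and both groups. Let f be the share of t already present in the Transition baseline, which is taken before dosing (Protocol 6.9). Let the groups otherwise be alike. These are simplifying assumptions.

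- Mean change, Transition: t − f·t = (1 − f)t
- Mean change, Add-On: t
- Unadjusted difference: −f·t
- Baseline difference: +f·t

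With b the slope of follow-up on baseline, the adjusted difference is the difference in mean change + (1 − b) × the baseline difference:

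−f·t + (1 − b)·f·t = −b·f·t

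This is non-zero whenever f, b and t are non-zero. For an assumed b of 0.7 to 0.9, baseline adjustment leaves 70% to 90% of the built-in difference.

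**2. Adjustment can also create a difference (illustration).** Assume zero mean change in both groups, equal variance at both times, a baseline gap D in SD units, and 55 and 65 subjects. The counts are those of the Efficacy Population (SAP 5.3); SAP Section 9 does not name the model population.

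- Spurious adjusted difference = (1 − b)·D
- SE = √(1 − b²) × √(1/55 + 1/65 + D²/118)
- D = 0.25, b = 0.9: difference 0.025, SE 0.081; chance of two-sided p < 0.05 about 6%
- D = 0.75, b = 0.7: difference 0.225, SE 0.140; chance about 36%

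The documents supply neither D nor b. The range shows that the mechanism is real, not what will happen in this trial.

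**3. Where the LS means are evaluated.** A pooled model with one baseline covariate usually evaluates LS means at the overall mean baseline. Each group's LS mean then differs from its value at its own mean baseline by slope × (overall mean − group mean), where slope is that of change on baseline. As an illustration only, take a 6MWD gap of 20 to 60 m, Transition lower, and a slope of −0.1 to −0.3. The shift is slope × gap × 65/120 for Transition, −1.1 to −9.8 m, and −slope × gap × 55/120 for Add-On, +0.9 to +8.3 m. Neither the gap nor the slope is in the documents.

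**4. Precision of the within-group estimate.** In SD units of change, before baseline adjustment and with complete data, approximate 95% half-widths are:

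- Transition: 1.96/√55 = 0.26
- Add-On: 1.96/√65 = 0.24
- Between-group contrast: 1.96 × √(1/55 + 1/65) = 0.36

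The within-group changes come from the models already planned.

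**5. MLWHF at Month 8.** SAP 9.4 and Protocol 6.10 schedule MLWHF at Baseline, Month 2, Month 4 and every 12 months thereafter, so the next scheduled visit is 4 + 12 = Month 16. SAP 9.4 nevertheless models change to Month 8 and names a Month 8 contrast. Values in the Month 8 window (Days 211 to 270, SAP 6.4) could come only from termination or off-schedule assessments.

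**The case against.** The strongest reply is that the SAP does not neglect within-group change. Sections 9.1 and 9.3 give it with 95% CIs, SAP 6.1 presents every summary table overall and by group, and the group-by-visit LS means come from the same fit as their contrast. This stands for 6MWD and NT-proBNP. A reader might infer that the contrast replaces the within-group analysis, and the documents do not support that. What remains is narrower: the MLWHF interval is missing, and the model-based change is a stated output for none of the three.

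Second, the section is headed exploratory, Protocol 6.1.2 says the study is not designed for efficacy conclusions, and SAP 6.1 discloses both the difference in treatment history and the lack of multiplicity control. This also stands and limits the weight of the point. It does not make the contrast answer an endpoint.

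Third, the absence of an efficacy objective would count against all of SAP Section 9, and the endpoints are listed for all patients rather than by group. That is fair. The case therefore rests on the endpoints being changes from baseline and on the confounding, not on the objectives alone.

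Fourth, within-group change is not clean either: baseline 6MWT is before dosing, later tests are 15 to 60 minutes after dosing (Protocol 6.9), and treatment is open label. That caveat should accompany the within-group results. The timing rule is common to both groups, but the Transition pre-dose state is on chronic treprostinil and the Add-On state is not.

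A reader might also infer a false-positive risk of 37% (1 − 0.95^9, nine contrasts) or 54% (1 − 0.95^15, all three MLWHF scores modelled). Those figures need independent true nulls. Here the visits are correlated, the MLWHF domains overlap with the total, and the null is not expected to hold. The point does not rely on them.

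**Conclusion.** The point holds in a limited form. As written, the only named product of three models is an inferential comparison of non-randomised groups whose baselines differ in treatment content. Baseline as sole covariate cannot correct that, and no endpoint uses the comparison. Labelling its results inferential also sits badly with Protocol 8.4. This conclusion follows from the group definitions and needs no numerical assumption.

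Its size in metres, NT-proBNP ratio or MLWHF points cannot be derived from the documents. The 70% to 90%, the 6% to 36% and the metre shifts above are illustrations under assumed slopes and baseline gaps. The consequence is confined to interpretation of exploratory endpoints; the primary safety analysis is untouched. The documents do not support a further inference that every between-group display must be banned: a clearly labelled descriptive one would do no harm. The change should be made, but the study's main result does not depend on it.

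**What to change.** - In SAP 9.1, 9.3 and 9.4, state that the main MMRM output is each group's LS mean change from baseline (ratio to baseline for NT-proBNP) with 95% CI at each visit. Evaluate it at that group's own mean baseline, or fit the model separately in each group.
- In SAP 9.4, add a within-group 95% CI to the MLWHF change summary and limit the MLWHF model to scheduled visits.
- Drop the between-group contrasts, or report them without p-values, labelled descriptive and confounded by prior treatment. Reword the last sentence of 9.3 to match.

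The cost is SAP wording and a changed estimate statement per model; no new data are needed. The inferential group comparison is lost or demoted, but no objective or endpoint uses it. Because Month 2 data have already been reported (SAP 2 and 5), the change should be recorded with its reason so that it does not look data-driven.
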